5.1.6. Study Drug Accountability

Upon receipt of the study drug(s), the investigator or designee will maintain accurate records of study drug delivery to the study center, the inventory at the study center, the use by each subject, the reconciliation of all study drug(s) received from the sponsor, and the return to the sponsor's or its designated depot/vendor of unused study drug(s).

Study personnel must ensure that all study drug supplies are temperature monitored and kept in a secure locked area with access limited to authorized personnel. This study product must not be used outside the context of this protocol. Under no circumstances should the investigator or site personnel supply study product to other investigators or clinics; or allow the supplies to be used other than as directed by this protocol.

The investigator and/or the responsible site personnel must maintain accurate records of the receipt of all study drug shipped by PTC or its designee, including, but not limited to, the date received, lot number, amount received, and the disposition of all study drug. Current reconciliation and dispensing records must also be maintained that include the date and amount of drug dispensed, and subject's assigned study number.

Unused clinical supplies must be returned to PTC or its designated depot/vendor after the study is completed. Accountability must be verified by the site monitor prior to return. Records documenting the date of study drug shipped, relevant sachet numbers, and amount shipped should be kept in the investigator site study file.

5.2. Measures to Minimize Bias: Randomization and Blinding

This is an open-label study.

5.3. Study Intervention and Compliance

Subject's parent(s)/caregiver(s) should return all remaining study drug (all unused sachets and drug kits) to the study site at Week 4 (Visit 3), Week 12 (Visit 4), and end of treatment (EOT) at Week 24 (Visit 5). The dosing sheet provided to subject's parent(s)/caregiver(s) will serve as a source document for subject compliance and will help the investigator determine how much unused drug should be returned upon study completion.

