5.1.2. Dosing and Administration

Subjects in the study will be administered ataluren 10, 10, 20 mg/kg (morning, mid-day, and evening dose, respectively), orally or via a NeoMed syringe. Dosing will be based on body weight, a common practice in pediatric studies that reduces variability in exposure by accommodating differences in subject size across the span of ages of the subjects who will participate in the clinical study. The subject's parent(s)/caregiver(s) will be provided a Study Drug Administration Record (dosing sheet) to document daily subject compliance.

5.1.2.1. *Dose and Dosing Regimen*

Dosing of ataluren will be on a milligram of drug per kilogram of subject body weight at baseline (Visit 2). A subsequent weight-based dose adjustment may be necessary over time (see Section 5.1.2.2). All subjects will receive approximately 10, 10, 20 mg/kg ataluren TID in the morning, at mid-day, and in the evening, respectively, for 24 weeks. Ataluren will be administered orally immediately after preparation.

The amount of study drug administered to each subject, any missed doses, and the reason for noncompliance will be recorded in the source documents and electronic Case Report Form (eCRF).

5.1.2.2. *Dose Adjustments and Modifications*

Because of changes in subject body weight over time, a weight-based dose adjustment may be necessary. Weight will be re-assessed at Week 12 and ataluren dosing adjusted accordingly.

5.1.2.3. *Schedule of Drug Administration*

Ataluren administration will begin at baseline (Visit 2) and continue for up to 24 weeks. As noted in [Table 1](#), three ataluren doses should be taken per day; the first dose in the morning, the second dose during the middle of the day (mid-day), and the third dose in the evening. Ideally each dose should be taken within ~30 minutes after a meal (eg, ~7:00 AM after breakfast, ~1:00 PM after lunch, and ~7:00 PM after dinner). Intervals for dosing should be ~6 hours (± 1 hour) between morning and mid-day doses, ~6 hours (± 1 hour) between mid-day and evening doses, and ~12 hours (± 1 hour) between evening doses and the morning dose on the next day. While it is realized that variations in dosing schedule may occur in the outpatient setting, the prescribed regimen (including dosing intervals and the relationship of dosing to meals) should be followed closely on the day preceding PK sample collection in the clinic.

Table 1: Suggested Daily Dosing

Dose Designation	Preceding Meal	Example Dose Times

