7. STUDY ASSESSMENTS AND PROCEDURES

7.1. Schedule of Events and Study Parameters

Subjects may be in the study for up to 4 weeks prior to receiving study drug at the baseline visit (Visit 2) and for 4 weeks \pm 7 days after last study drug administration (Visit 5).

The timing and types of procedures and assessments for this study are specified below in [Table 2](#).

Table 2: Schedule of Assessments

Study Period	Screening ^a	Baseline/ Start of Treatment ^b	Treatment Phase		EOT/ET ^c	Post- Treatment Follow-Up/ EOS ^d
Visit	Visit 1	Visit 2^e	Visit 3^e	Visit 4	Visit 5^e	Visit 6
Week	-	Week 0	Week 4	Week 12	Week 24	Week 28
Visit Window (days)	(-28 to -1)	0	±7	±7	±7	±7
Eligibility						
Informed Consent ^f	X					
Inclusion/Exclusion	X	X				
Medical/Surgical History	X	X				
Demographics	X					
Safety Assessments						
Physical Examination ^g	X	X	X	X	X	
Clinical Labs ^h	X	X	X	X	X	
Blood Sample for Gene Sequencing ⁱ	X					
Height/Weight/BMI	X	X	X	X	X	
Vitals (HR and BP) ^k	X	X	X	X	X	
ECG ^l	X	X	X		X	
AE/SAE Monitoring	X	X	X	X	X	X
Concomitant Medications ^m	X	X	X	X	X	X
PK Blood Sampling (VAMS) ⁿ		X	X		X	
Blood/Plasma Partition Sampling ^o		X	X		X	
Study Drug Administration						
Dispense Drug		X		X		
Unused Drug Return/Compliance			X	X ^p	X	

Abbreviations: AE, adverse event; BMI, body mass index; BP, blood pressure; CL/F, apparent clearance; C_{trough}, trough concentration (plasma concentration pre morning dose); ECG, electrocardiogram; EOS, end of study; EOT, end of treatment; ET, early termination; HR, heart rate; PK, pharmacokinetic; SAE, serious adverse event; VAMS, volumetric absorptive microsampling

^a Screening procedures must take place within 28 days of baseline (Visit 2).

^b Any screening procedure completed within and including 14 days of baseline (Visit 2) can serve as baseline assessment and does not need to be repeated at Visit 2.

^c Subjects who terminate the study early are to complete all assessments required for EOT/ET (Visit 5) prior to leaving the study and will be contacted by phone 4 weeks from the final dose of study medication for the post-treatment follow-up/EOS (Visit 6).

^d Post-treatment follow-up will be conducted by phone 4 weeks ± 7 days from last day of study treatment for review of adverse events and concomitant medications. Post-treatment follow-up is not required if subjects are transitioning to another ataluren clinical trial.

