ⁿ PK samples (VAMS method) will be drawn at baseline (Visit 2), Week 4 (Visit 3), and Week 24 (EOT/ET) for evaluation. Samples will be drawn immediately pre-dose, and at 1-, 2-, 3-, and 4-hours post-dose following both the morning and mid-day doses and immediately pre-dose and at 1-, 2-, 3-, 4-, and 12- (before the next day morning dose) hours post-dose following the evening dose.

^o Blood sampling via venous draw will be conducted at Visits 2, 3, and 5. These additional samples will be taken at 2.5 -hours and 4.5 -hours post morning dose (1.5 ml each timepoint). Out of the 1.5 mL blood sample collected, at the 2.5 hour and 4.5 hour timepoints, 1 mL blood sample will be processed to plasma and the remaining 0.5 mL blood will be processed to dried blood sample using a VAMS device.

^p Parent(s)/caregiver(s) will record daily dose administration on a Study Drug Administration Record (dosing sheet) and Subjects are required to return any unused study drug.

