7.4. Study Drug Administration Procedures

7.4.1. Study Drug Administration

Ataluren will be supplied at baseline and Week 12 (Visit 4). Because of potential changes in subject body weight over time, the subject's body weight will be assessed and documented at Week 12 and dose modifications made as appropriate.

The PTC medical monitor should be notified of any AE or laboratory abnormality that leads to dose interruption and should be apprised of ancillary laboratory or other diagnostic findings and the evolving data from any work-up of the initial abnormality. The return of any unused drug sachets will be documented for compliance assessments. The subject's parent(s)/caregiver(s) will return all unused sachets of ataluren as instructed for full compliance assessments.

Please see Section [5](#) for further information on Study Intervention Procedures, including study intervention and compliance.

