5.2. Duration of Treatment with Study Drug

Duration of treatment with study drug during study will be calculated as:

Duration (days) = Date of last dose of study drug - Date of first dose of study drug + 1

Duration of treatment with study drug in days will be presented in by-subject listing only on safety population.

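### Does the return of all unused study drug at Week 4, with no supply until Week 12, leave subjects without drug for eight weeks?

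*Protocol*

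**What the plan says.** Protocol 5.3, on compliance, states that caregivers "should return all remaining study drug (all unused sachets and drug kits) to the study site at Week 4 (Visit 3") and names Week 12 and end of treatment at Week 24 in the same sentence. Its next sentence says that the dosing sheet "will help the investigator determine how much unused drug should be returned upon study completion".

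Protocol 7.4.1 gives the supply points: "Ataluren will be supplied at baseline and Week 12 (Visit 4"). It also gives the reason for returns: caregivers "will return all unused sachets of ataluren as instructed for full compliance assessments".

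Table 2 in Protocol 7.1 marks the dispensing row at Visits 2 and 4. It marks the row "Unused Drug Return/Compliance" at Visits 3, 4 and 5. Footnote p, which says "Subjects are required to return any unused study drug", is attached to the Visit 4 cell only; the Week 4 cell is a plain X. SAP Appendix 1 repeats the same pattern.

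Protocol 5.1.2.1 prescribes dosing "in the morning, at mid-day, and in the evening, respectively, for 24 weeks".

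**The concern.** Section 5.3 treats three visits alike, but they differ in what comes next. At Week 12 a full return is followed by new supply. At Week 24 treatment ends. At Week 4 neither applies, and dosing three times a day is meant to continue. The Week 4 visit description (Protocol 7.1.3), the preparation instructions (5.1.5), the accountability section (5.1.6) and the Table 2 footnotes contain no hand-back or re-issue step.

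If a site kept the drug at Week 4, its subjects would be untreated until Week 12. The Week 12 laboratory values summarized under SAP 8.2 would then be taken off drug, and off-drug time would count within the treatment-emergent window of SAP 8.1. With 6 to 10 subjects at up to 3 sites, even one site acting this way would show in a summary.

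**Working it through.** The plan states no figure for drug supply, so there is none to reproduce. The check computes coverage under each reading and then asks which reading the text supports.

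**Inputs**
- Supply points: Weeks 0 and 12 (Protocol 7.4.1; Table 2; SAP Appendix 1).
- Return points: Weeks 4, 12 and 24 (Protocol 5.3; Table 2).
- Treatment period: 24 weeks, 3 doses a day (Protocol 5.1.2.1 and 5.1.2.3).
- Windows at Visits 3 and 4: ±7 days each (Table 2).
- Quantity dispensed: not given. Assumption: each supply is meant to last to the next supply point or to end of treatment.

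**Reading A: counted at Week 4 and handed back**
- Coverage = (12 − 0) + (24 − 12) = 24 weeks.
- Gap = 24 − 24 = 0 weeks.

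**Reading B: surrendered at Week 4**
- Nominal gap = 12 − 4 = 8 weeks, and 8/24 = 33% of the period.
- In doses: 8 × 7 × 3 = 168 per subject.
- Shortest gap with windows: (12 − 1) − (4 + 1) = 6 weeks.
- Longest gap with windows: (12 + 1) − (4 − 1) = 10 weeks.

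**Which reading fits the text**

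| Place | Bearing |
|---|---|
| Protocol 7.4.1, supply | Names two supply points; does not say they are the only times a caregiver may leave with drug |
| Protocol 7.4.1, return | Gives compliance assessment as the purpose |
| Protocol 5.3, second sentence | Places the reckoning of drug to be returned at study completion |
| Table 2 | Return and compliance share one row; the footnote requiring return is on the Visit 4 cell |
| Protocol 5.1.6 | Unused supplies go to the sponsor or its depot after the study is completed; re-issue is not barred |
| Protocol 5.1.2.1 | 24 weeks of dosing, with no planned break |
| Protocol 5.4.2, 6.1, 6.2 and 7.4.1 | Interruption or withdrawal is tied to specific grounds; a drug count is not one |

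Reading B needs two premises that the text does not supply: that return means permanent surrender, and that supply includes handing back a subject's own counted sachets. Without both, the sections agree.

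**What would reach the analysis under Reading B**
- Duration: SAP 5.2 counts last dose date minus first dose date plus 1, so a break in the middle would not change it. In addition, "Duration of treatment with study drug in days will be presented in by-subject listing only on safety population".
- Interruptions: SAP 5.3 lists start and stop dates with reasons, so a break would be visible by subject.
- Week 12 laboratory summaries and adverse event timing: affected for those subjects.
- PK: there is no profile at Week 12, and the Week 24 profile would follow 24 − 12 = 12 weeks on the second supply.

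**The case for a change.** The strongest opposing argument is that the parenthesis in 5.3, covering all unused sachets and kits, leaves no ordinary sense in which a caregiver keeps anything, so the step that keeps treatment continuous is left to inference. Section 5.1.6 also requires dispensing records with dates and amounts, and nothing says whether a Week 4 hand-back counts as dispensing. Up to 3 sites might log it differently. A study manual or written dosing instructions may cover the step, but they are not among the documents and would not alter the protocol's wording.

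It stands that the hand-back is unwritten and that 5.3 is loosely worded. Differences in site drug logs are possible. They would not carry into the results. The dosing sheet is the compliance source under 5.3, and Protocol 8.5.6 and SAP 5.3 present administration data as by-subject listings. The argument does not show that a site would withhold a child's study drug for eight weeks against the stated regimen.

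**Conclusion.** No change is called for. Taken together, the sections describe drug brought in for a count at each treatment visit, with new supply at baseline and Week 12. On that reading coverage is 24 of 24 weeks. The 8-week figure (6 to 10 with windows) describes a reading that the rest of the protocol does not support, so it should not be quoted as a loss of exposure.

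This rests on two assumptions: that each supply is sized to reach the next supply point or end of treatment, and that sites return counted sachets to the family at the Week 4 overnight visit. If a site did otherwise, the SAP 5.3 listing would show it. The primary safety endpoint, the Week 24 PK endpoint, the CK change, the two analysis populations and the descriptive methods are defined independently of this step. Whether to align the wording of 5.3, 7.4.1, Table 2 and SAP Appendix 1 is an editorial matter for the sponsor.

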5.4. Concomitant Therapy

Other than the study drug, any treatments (including prescription and non-prescription drugs, health foods, herbal remedies, or self-prescribed drugs) that are taken by or given to a subject during the screening period, during study drug administration, and for 4 to 6 weeks after discontinuation of study drug are considered concomitant medications.

To the extent possible, administration of any treatment other than the study drug is to be minimized during the study period. The subject's parent(s)/caregiver(s) are discouraged from providing "health supplements" (eg, creatine, glutamine, coenzyme Q), herbal remedies, growth hormone, or self-prescribed drugs, at any time during the study.

If considered necessary for the subject's well-being, drugs for concomitant medical conditions or for symptom management may be given at the discretion of the investigator. The decision to authorize the use of any other drug(s) must take into account subject safety, the medical need, the potential for drug interactions, the possibility for masking symptoms of a more relevant underlying event, and whether use of a concomitant medication would compromise the outcome or integrity of the study.

The subject's parent(s)/caregiver(s) will be instructed about the importance of informing the clinic staff of the subject's use of any drugs or remedies (whether prescribed, over the counter, or illicit) before and during the course of the study. Information regarding all concomitant medications will be collected and documented in the concomitant medication page of the eCRF and in the source documents by the clinic staff. Concomitant therapies will be recorded, reviewed, and updated at each visit.

Any new concomitant therapy or modification of an existing therapy can be linked to an AE. A corresponding AE Form is to be completed to account for the change in therapy, except in some cases, such as therapy used for prophylaxis and dose modification for a chronic condition.

5.4.1. Concomitant Use of Corticosteroids

Although it is recognized that corticosteroid use has demonstrated benefit in DMD patients, because of their potential to influence changes in BP measurements and cholesterol and triglyceride levels, corticosteroid use is strongly discouraged in this study in order to minimize potential confounding effects on the interpretation of study results. If the investigator deems it necessary for the benefit of the subject to continue use of a corticosteroid during the study, a stable and standardized regimen must be maintained for at least 30 days prior to randomization, and throughout the duration of the study.

5.4.2. Concomitant Use of Systemic Aminoglycoside Therapy and/or Intravenous Vancomycin

Ataluren should not be co-administered with IV aminoglycosides. Cases of decreased renal function were observed in a clinical study of subjects with nonsense mutation cystic fibrosis receiving concomitant ataluren and IV aminoglycosides (as described in the Ataluren IB).

In subjects who require treatment for serious infections, investigators should substitute other antibiotics for systemic aminoglycosides when clinically appropriate. If IV aminoglycosides or other nephrotoxic antibiotics (eg, vancomycin) are administered, study drug must be interrupted during the course of these antibiotics. Subjects requiring IV aminoglycoside or vancomycin therapy should be closely monitored in an appropriate setting, such as a hospital. In subjects receiving potentially nephrotoxic agents such as IV aminoglycosides or vancomycin, antibiotic drug levels and serum creatinine and BUN should be followed closely. The antibiotic trough level and creatinine and BUN should be measured within 24 to 48 hours of administration of the first antibiotic dose, and further antibiotic dosing should be based on these results. Trough levels should be measured at intervals during antibiotic treatment. Creatinine and BUN should be measured prior to initiating IV aminoglycoside or vancomycin therapy and at least twice a week during the course of treatment.

5.4.3. Coumarin-Based Anticoagulants

As the primary route of ataluren metabolism is via glucuronidation by UGT1A9, clinically significant interactions between ataluren and co-administered drugs metabolized by cytochrome P450 (CYP) enzymes are unlikely. In particular, ataluren is not an inhibitor of CYP1A2, CYP2B6, CYP2C8, CYP2C9, CYP2C19, CYP2D6, and CYP3A4/5, and does not have induction potential on the major CYP enzymes. Based on in vitro studies, ataluren is also not expected to be an inhibitor or a substrate of p-gp mediated transport.

As an added measure of safety, investigators should pay specific attention to use of drugs that are known substrates of this enzyme, particularly when such drugs may have a low therapeutic index.

Drugs that are metabolized by CYP2C8 or CYP2C9 that have low therapeutics indices (in particular, paclitaxel for CYP2C8 and coumarin anticoagulants [eg, warfarin], phenytoin, or tolbutamide for CYP2C9) may be of particular concern. Coumarin anticoagulants are cleared by CYP2C9 and increases in plasma concentrations of coumarin anticoagulants may result in serious clinical consequences. For subjects who require anticoagulation during the study, use of an alternative form of anticoagulation (eg, fractionated heparin) should be considered. Phenytoin is metabolized by CYP2C9 and concomitant use with ataluren may be of potential concern. For subjects who require anticonvulsant therapy during the study, use of alternative anticonvulsant drugs should be considered.

The metabolism of losartan to its active metabolite may, in part, be mediated by CYP2C9. However, concomitant use of losartan and inhibitors of CYP2C9 have not been examined. Because this drug does not have a narrow therapeutic window, the potential for mild to moderate changes in activity does not require a dose modification.

5.4.4. Inducers of UGT1A9 or Substrates of OAT1, OAT3, or OATP1B3

Based on in vitro studies, ataluren is a substrate of UGT1A9 and breast cancer resistant protein (BCRP). Caution should be exercised when ataluren is co-administered with drugs that are inducers of UGT1A9 (eg, mycophenolate mofetil, rifampicin), or inhibitors of BCRP (eg, cyclosporine).

In vitro data indicate that ataluren is an inhibitor of UGT1A9, organic anion transporter 1 (OAT1), organic anion transporter 3 (OAT3) and organic anion transporting polypeptide 1B3 (OATP1B3). Caution should be exercised when ataluren is co-administered with drugs that are substrates of UGT1A9 (eg, propofol, mycophenolate mofetil), OAT1, OAT3, or OATP1B3 (eg, oseltamivir, acyclovir, ciprofloxacin, captopril, furosemide, bumetanide, valsartan, pravastatin, rosuvastatin, atorvastatin, pitavastatin) because of the risk of increased concentration of these drugs.

6. STUDY INTERVENTION DISCONTINUATION AND PARTICIPANT DISCONTINUATION/WITHDRAWAL

6.1. Discontinuation of Study Intervention

If after appropriate consideration of study drug interruption/modification and consultation with the PTC medical monitor, it is not appropriate for a subject to continue with study treatment, then study drug should be permanently discontinued. After permanent discontinuation of study drug for a safety concern, and if the initial event was reported as a SAE, then a follow-up SAE report form should be completed. In the case of a treatment discontinuation due to an event that is not an SAE, the PTC medical monitor should be notified. In addition, details regarding the reasons for discontinuation and the AEs leading to the discontinuation should be recorded in the source documents and in the appropriate Case Report Form (CRF). The Early Termination (ET) Visit CRF should be completed and appropriate follow-up, ie, at ~4 weeks as per protocol or until recovery from or stabilization of the AE, whichever comes last.

6.2. Participant Discontinuation/Withdrawal from the Study

All subjects who receive ataluren should remain in the study whenever possible. However:

1. The subject's parent(s)/caregiver(s) has the right to withdraw consent and discontinue ataluren at any time.
2. If the subject's condition substantially worsens after initiating ataluren, the subject will be carefully evaluated by the investigator. The subject will be withdrawn from treatment if continuing would place them at risk.
3. The investigator may withdraw the subject from ataluren, if, in the investigator's clinical judgment, it is not in the subject's best interest to continue.
4. In the event the subject becomes significantly noncompliant with ataluren administration, study procedures, or study requirements, the subject should be withdrawn from ataluren when the circumstances surrounding noncompliance increase risk to the subject or are anticipated to substantially compromise the interpretation of study results.
5. This study may be discontinued by the relevant regulatory authority, Institutional Review Board/Independent Ethics Committee (IRB/IEC), and/or PTC at any time.

